Efficacy and Outcomes Research Assessments¹²					
Assessments of migraine pain, migraine symptoms (phonophobia, photophobia, and nausea) and functional disability ¹⁴			X	X	
MQoL (Migraine Quality of Life Questionnaire) ¹⁴				X (24-hour assessment)	
Preference of Medication (PoM) ¹⁴				X (24-hour assessment)	

¹ **Screening Phase** will be 3 - 28 days. Subject should be entered in the IWRS after they sign the informed consent form to obtain their study subject identification code.

² The **Baseline/ Randomization Visit** may only occur *after* all screening procedures are completed and the subject meets all inclusion/exclusion criteria. If the subject does not meet all eligibility requirements, the subject should be screen failed in the IWRS. Subjects may be re-screened with a new subject ID.

³ Subjects will use their assigned eCOA handheld device before study drug administration to answer questions about their migraine symptoms upon experiencing a moderate or severe migraine headache. The subject will administer zavegepant or matching placebo if the following criteria are met: 1) the headache remains moderate or severe; 2) the subject has completed all required migraine assessment questions in the handheld, including their current most bothersome migraine symptom, and 3) the subject has not already taken prohibited medications.

⁴ Subjects should keep track of their concomitant medications on the IRB approved study paper diary provided throughout the study. A concomitant medication paper diary will be provided to subjects at the Screening visit. These paper diaries should be returned to the investigational site at each visit for review and electronic data capture (EDC) entry. The paper diaries should be kept as source documents.

⁵ Subjects should keep track of their rescue medications on the IRB approved study paper diary provided throughout the study. A rescue medication paper diary will be provided to subjects at the Baseline visit. Reference the rescue medication section 5.5 for additional information. These paper diaries should be returned to the investigational site for review and electronic data capture (EDC) entry. The paper diaries should be kept as source documents.

⁶ The randomization visit is considered day 1 out of the 45 days subjects have to treat and report a migraine in their handheld device. Subjects will be randomized in the IWRS and will be stratified by answering “yes” or “no” to prophylactic migraine medication use in the IWRS.

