2 STUDY DESCRIPTION

2.1 Study Design

BHV3500-301 is a Phase 3, double-blind, randomized, multicenter, outpatient evaluation of the safety and efficacy of zavegepant versus placebo in the treatment of moderate or severe migraine.

[figure not shown]
The design of the study is shown in [Figure 1](#). After providing informed consent, subjects first participate in the screening phase (28-day period) to determine eligibility for the study. Approximately 1,750 subjects are screened to randomize approximately 1,400 subjects to study medication (zavegepant or placebo). The study drug zavegepant (BHV-3500) is formulated as 10 mg intranasal (IN) or matching placebo. Randomization is stratified by IWRS prophylactic migraine medication use (yes or no).

Per protocol, subjects in this study may be randomized only once.

After randomization, study medication is dispensed to subjects to take home for up to 45 days. Subjects are dispensed one Aptar Unit Dose System (UDS) liquid spray device containing a single dose of study medication zavegepant or a matching placebo. Subjects are instructed to take their study medication as an outpatient, when they have a migraine headache which reaches moderate or severe pain intensity. Subjects are instructed by an electronic diary (eDiary) to take study medication after a migraine attack of moderate or severe pain intensity. Subjects complete an eDiary for up to 48 hours after taking the study medication. Subjects also record efficacy and outcomes research data in their eDiary.

Subjects return to the study site within 7 (\pm 2) days of study treatment for review of the eDiary, assessment of medication compliance, and monitoring of tolerability and safety. If a subject has NOT experienced a migraine headache of moderate or severe pain intensity within 45 days after randomization, they still are required to complete all EOT visit procedures and return unused study medication and eDiary to the investigational site.

Figure 1: Study Schematic

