6.2.5 Baseline Characteristics

Baseline characteristics include (1) demographics and other relevant baseline characteristics, (2) baseline disease characteristics (i.e., migraine history, cardiac and other risk factors, prior triptan response, current triptan response, and migraine characteristics at the time of dosing), (3) medical history, and (4) prior non-study medications. These are detailed in Sections 6.2.5.1 through 6.2.5.4, respectively.

Baseline characteristics are tabulated for each of the following analysis sets as follows:

- Efficacy analysis set: Baseline characteristics (1) through (4) by as-randomized treatment group and overall to support efficacy
- Safety analysis set: Baseline characteristics (1) through (4) by as-treated treatment group and overall to support safety

- Subjects in the enrolled analysis set but not in the full analysis set: Demographics and other relevant baseline characteristics, and migraine history by overall only
- Subjects in the full analysis set but not in the efficacy analysis set: Demographics and other relevant baseline characteristics, and migraine history by as-randomized treatment group and overall.

IWRS prophylactic migraine medication use at randomization (yes, no) is tabulated by as-randomized treatment group and overall for the randomized analysis set.

Baseline for a parameter (e.g., weight) is defined according to analysis set as follows:

- Enrolled analysis set but not in the randomized analysis set: Last non-missing value
- Randomized analysis set but not in the safety analysis set: Last non-missing value at or before the IWRS randomization date
- Efficacy, safety, and outcomes research analysis sets: Last non-missing value in the pre-treatment analysis period; see Section 7.2).

“Last” is determined by the measurement date/time. Other criteria such as last entry date/time or laboratory test source may be applied to break ties on the same measurement date, as available from CRF data. See Sections 6.4.2.3, 6.4.3.1, and 6.4.4.1 for handling of ties on the same measurement date or time.

By-subject listings are provided for the enrolled analysis set for the following: demographics; medical history; migraine history; cardiac and other risk factors for subjects with any risk factor present; prior triptan response; and current triptan response. Refer to the Zavegepant Core SAP for additional details.

6.2.5.1 *Demographics and Other Relevant Baseline Characteristics*

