Refer to the Zavegepant Core SAP for additional details.

LFT Elevations: Cumulative, Mutually Exclusive, and Composite

The number and percentage of subjects with LFT elevations are tabulated separately for each analysis period (pre-treatment, on-treatment) for the safety analysis set. LFT elevations are based on fold changes above ULN.

LFT ULN Shifts from Baseline to Worst Elevation

LFT ULN shifts from baseline to the worst (highest) on-treatment LFT elevation are tabulated as the number and percentage of subjects in the safety analysis set in pre-specified elevation categories.

eDISH Scatter Plot

An evaluation of drug-induced serious hepatotoxicity (eDISH) scatter plot displays the maximum TBL ratio of value to ULN on the y-axis versus the maximum ALT ratio of value to ULN on the x-axis by treatment group, where both maxima are on treatment but not necessarily concurrent.

6.4.2.3 *Laboratory Test Changes from Baseline*

Values and changes from baseline in laboratory tests are tabulated as continuous variables at baseline and the end of treatment visit.

If a subject has multiple values in the end of treatment analysis visit window, then a single value is selected using the following hierarchy as available:

- Non-missing viable value collected last. If there are multiple viable values on the same date, then the following hierarchy is used as available:
 - Last central laboratory test value collected timewise with the last accession identifier.
 - Last local laboratory test value entered.

Viable laboratory test values are defined as those from (1) kits from the central laboratory that are not expired (see Section 6.4.2), or (2) local laboratory tests reported on CRFs.

- Non-missing value from an expired kit from the central laboratory collected last. If there are multiple values on the same date, then the value with the last accession identifier is used.

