6.6.2 COVID-19 Impact over Time

COVID-19 visit impact is tabulated by analysis visit (Screening, Randomization, End of Study) and as-treated treatment group for the safety analysis set. The number and percentage of subjects in the categories defined by COVID-19 visit impact type, COVID-19 visit impact relationship are presented for each analysis visit. Percentages are based on subjects with ≥ 1 visit with non-missing COVID-19 visit impact in the analysis visit window.

Missing LFT data impacted by COVID-19 are tabulated at each analysis visit for the safety analysis set as the number and percentage of subjects in the following categories:

- 1) Missing LFT data, defined as missing values for all of the 4 following LFTs in the analysis visit window: ALT, AST, ALP, and TBL.
- 2) Missing LFT data at visits impacted by COVID-19, i.e., meeting criteria (1) and having ≥ 1 visit impacted by COVID-19 in the analysis visit window (see Section 9.1.3)
- 3) Missing LFT data at missed visits due to COVID-19, i.e., meeting criteria (1), (2), and having ≥ 1 missed visit in the analysis visit window (see Section 9.1.1).

Percentages are based on evaluable subjects at each analysis visit. A subject is evaluable at an analysis visit if the study day corresponding to the last contact date is \geq lower bound of the analysis visit window. For subjects who took study drug but were not randomized, the treatment day corresponding to the last contact date is used instead.

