7.2 Analysis Periods

Analysis periods are defined as follows:

- Pre-treatment: measurement date/time at or before the study drug start date/time. This period is used to derive baseline values and to assess pre-treatment endpoints. Note that all measurements are pre-treatment for subjects in the enrolled analysis set with missing study drug start date.
- On-treatment: measurement date/time after the study drug start date/time. This period is used to assess safety endpoints on treatment. Note that AEs with imputed start date equal to the study drug start date are part of this period.

See Section 7.1 for derived date/times for determining analysis periods.

If measurement time is missing, not collected, or not applicable for a parameter, then the measurement date is compared to the derived date.

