7.3 Analysis Visit Windows

Study days are calculated from the IWRS randomization date as follows:

- Measurement date – randomization date + 1, if measurement date \geq randomization date
- Measurement date – randomization date, if measurement date $<$ randomization date.

Treatment days are calculated from the study drug start date as follows:

- Measurement date – study drug start date + 1, if measurement date ≥ study drug start date
- Measurement date – study drug start date, if measurement date < study drug start date.

Analysis visit windows for safety parameters are presented in [Table 4](#).

Table 4: Analysis Visit Windows for Safety Parameters

Analysis Visit	Analysis-Specified Interval
Screening	
 • ≤ Study day -1 or {both study day and treatment day missing} • ≤ Treatment day -1 *
Randomization	Study day 1
End of treatment	
 • ≥ Study day 2 • ≥ Treatment day 1 *

* Applies only to subjects who took study drug but were not randomized

See Section [7.5.2](#) for efficacy analysis windows and Section [7.5.3](#) for outcomes research analysis windows.

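### For randomised subjects the end-of-treatment safety window overlaps the pre-treatment period, so in rare cases one pre-dose record can serve as both baseline and end-of-treatment value

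*SAP*

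**What the plan says.** **Window.** SAP Section 7.3 sets the origin: "Study days are calculated from the IWRS randomization date as follows". Table 4 then defines End of treatment as study day 2 or later, with no upper limit. A second line, treatment day 1 or later, carries the footnote "Applies only to subjects who took study drug but were not randomized".

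**Time to dosing.** A footnote to Table 1 of the protocol states: "The randomization visit is considered day 1 out of the 45 days subjects have to treat and report a migraine in their handheld device". SAP Section 2.1 agrees: "study medication is dispensed to subjects to take home for up to 45 days".

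**Baseline.** SAP Section 7.2 defines pre-treatment as "measurement date/time at or before the study drug start date/time". Where no clock time is available, dates are compared. For the safety analysis set, Section 6.2.5 takes baseline as the "Last non-missing value in the pre-treatment analysis period".

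**Choosing the end-of-treatment value.** For laboratory tests, Section 6.4.2.3 applies a hierarchy when several values lie in the window. The first choice is "Non-missing viable value collected last", where viable means an unexpired central kit or a local laboratory result. An expired-kit value comes second. Neither step mentions the on-treatment period. For other parameters, Section 6.4 takes the last value in the analysis period when there are several, without saying which period is meant.

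**Missing liver tests.** Section 6.6.2 tabulates missing LFT data by analysis visit, "defined as missing values for all of the 4 following LFTs in the analysis visit window".

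**The concern.** The window label promises a postdose result, but for randomised subjects its definition does not refer to the dose. From day 2 until dosing, a record meets the definition of a pre-treatment value and also lies in the End of treatment window. If that record is selected for both roles, the table shows a change of exactly zero for a subject about whom it has no usable postdose information.

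Laboratory tests are the clearest case. Their hierarchy ranks any viable value above any expired-kit value, so a pre-dose retest can displace a sample actually drawn after dosing.

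For liver tests the stake is different. A treated subject with no postdose ALT, AST, ALP or TBL, but with any one of them measured between day 2 and the dose, is not counted as missing. The second and third rows of that table are nested in the first, so the subject drops out of all three.

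**Working it through.** The plan states no figure on this point, so the check applies the written rules literally.

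**1. Length of the overlap.** With dosing on study day d, the full days before the dosing day that lie in both periods run from day 2 to day d − 1, which is d − 2 days.

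| Dosing day d | d − 2 |
|---|---|
| 2 | 0 |
| 10 | 8 |
| 30 | 28 |
| 45 | 43 |

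If d is 2 or later, a date-only record on the dosing date itself is also in both. It is pre-treatment under Section 7.2 and in the window under Table 4. Vital signs (Section 6.4.3) and local laboratory results (Section 6.4.2) are recorded by date only.

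**2. Traced laboratory examples.** The values are assumed for illustration: 40 at screening (day −14), 55 at an unscheduled test on day 10, dosing on day 30, and 70 at the end-of-treatment visit on day 37. Baseline is the last value up to the dose. The end-of-treatment value is the last viable value from day 2 on, or failing that the expired-kit value. Change = end-of-treatment value − baseline.

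| Case | Baseline | End of treatment as written | Change as written | Change if only on-treatment values count |
|---|---|---|---|---|
| Interim test, viable postdose value | 55 | 70 | +15 | +15 |
| Interim test, no postdose value | 55 | 55 (day 10) | 0 | missing |
| Interim test, postdose kit expired | 55 | 55 (day 10) | 0 | 70 − 55 = +15 |
| No interim test, viable postdose value | 40 | 70 | +30 | +30 |
| No interim test, postdose kit expired | 40 | 70 | +30 | +30 |

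The written rule fails only in the second and third cases. Both need an interim value, together with an absent or expired-kit postdose value.

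**3. Other parameters.** The third case cannot arise for vital signs, ECG or S-STS, because kit expiry plays no part there. The second case can arise unless the analysis period in Section 6.4 means on-treatment and also governs a single value. That sentence is written only for multiple values.

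**4. Where interim values could come from.** Table 1 of the protocol schedules laboratory tests and ECG at Screening and End of Treatment, and vital signs at Screening, Baseline and End of Treatment. Nothing of this kind is scheduled between day 1 and dosing. What remains is unscheduled testing. Protocol Section 6.3.4 asks for clinically significant abnormal results to be repeated until resolved, Section 6.3.4.1 allows reflex tests after the baseline visit, and SAP Section 9.1.1 foresees unscheduled visits.

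**5. Where postdose values could be lost.** Protocol Section 4.3.5 allows parts of the end-of-treatment visit to be done remotely, and the COVID-19 form (SAP Section 9.1.1) records missed visits and incomplete assessments. SAP Section 6.4.2 says that the central laboratory identifies expired kits.

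**6. Outputs that do not use the window.** The following are restricted to on-treatment data:
- worst laboratory abnormality, toxicity-grade shifts and low/normal/high shifts (6.4.2.1);
- on-treatment LFT elevations, ULN shifts and the eDISH plot (6.4.2.2);
- vital-sign abnormalities (6.4.3.2);
- ECG shifts and abnormalities (6.4.4.2 and 6.4.4.3).

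**The case against.** The strongest reply is that this almost never happens and touches nothing that matters. Much of that stands. No safety measurement is scheduled in the overlap. The bilirubin and aminotransferase retests required for eligibility belong to the screening period (protocol Section 5.3), so they fall before the window. With no laboratory draw planned between Screening and End of Treatment, little would prompt a repeat before dosing. The protocol's laboratory safety endpoints (Section 9.3.2) are frequencies of abnormalities and LFT elevations, which the SAP takes from on-treatment data. The by-subject listings flag on-treatment records, so a pre-dose value could be seen there.

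A second reply is that Section 6.4 already confines non-laboratory selection to the analysis period, most naturally on-treatment, and refers to the Zavegepant Core SAP for slotting into periods. The first part is a real but incomplete safeguard, because the period is not named and single values are not covered. The Core SAP was not available for this check. It is cited for analysis periods, whereas the visit windows are defined in Table 4. Neither part helps with laboratory tests, for which Section 6.4 says that a different algorithm applies.

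A reader might infer that any unscheduled value between randomisation and dosing yields a zero change. It does not, because a viable postdose value is later and is selected. A reader might also put a rate on the problem, say 1% to 2% of 1,260 subjects (12.6 to 25.2, or about 13 to 25). The documents give no such rate, and 1,260 is the planned number evaluable for efficacy, not a count of treated subjects.

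**Conclusion.** The rule is wrong as written but rarely triggered. An error requires an unscheduled value between day 2 and the dose, and in addition either no postdose value or, for laboratory tests only, an expired postdose kit with a viable pre-dose value. The end-of-treatment value is then a pre-dose record and the change is exactly zero, so the error leans towards no change. The missing-LFT table can be wrong in the first situation only, since a subject with an expired postdose kit does have postdose liver tests.

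The effect is confined to the descriptive end-of-treatment and change-from-baseline tables and the missing-LFT table. Efficacy, adverse events and the on-treatment abnormality, shift and eDISH outputs are not affected, so the documents do not support a wider doubt about the safety conclusions. The number of subjects cannot be derived from the documents. The conclusion rests on a literal reading of Sections 6.2.5, 6.4, 6.4.2.3, 7.2 and 7.3, and on the Core SAP containing no overriding restriction. It is firm for laboratory tests on the supplied text and weaker for other parameters, where Section 6.4 gives partial protection.

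**What to change.** 1. Leave Table 4 as it is for slotting visits. COVID-19 visits are also assigned by it (Sections 6.6 and 9.1.5.2), and moving the window to the dose would leave visits between day 2 and dosing without an analysis visit. It would also disturb the Section 6.6.2 denominator, which compares the study day of last contact with the window's lower bound.
2. In Sections 6.4 and 6.4.2.3, state that the end-of-treatment value, whether one or several are available, is selected only from values in the on-treatment period of Section 7.2. An on-treatment expired-kit result then ranks above any pre-dose result.
3. Refer to the on-treatment period, not to treatment day 1 or later. A date-only record on the dosing date is treatment day 1 but pre-treatment under Section 7.2, so the treatment-day wording would bring the overlap back.
4. In Section 6.6.2, define missing end-of-treatment LFT data for treated subjects as having no on-treatment value for any of ALT, AST, ALP and TBL.

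The cost is minor programming changes. No new data are needed and no tested endpoint changes. Affected subjects without a postdose value would correctly appear as missing.

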7.4 Duplicate Subjects

Duplicate subjects are those who re-screened once in study BHV3500-301 (per protocol), and are assigned more than 1 subject identifier. These subjects are identified from the Informed Consent/Demographics CRF, which captures the previous subject identifier. The following conventions apply:

- The unique subject identifier is derived as per the latest version of Biohaven Dataset Guidelines.
- The raw datasets contain data from all BHV3500-301 subject identifiers, with the unique subject identifier populated across records.
- The analysis datasets contain data as follows:
 - If the subject is in the full analysis set, then only data from the subject identifier corresponding to randomization or treatment in study BHV3500-301 are included.
 - If the subject is not in the full analysis set, then only data from the subject identifier corresponding to the last enrollment in study BHV3500-301 are included.
 - The unique subject identifier and previous BHV3500-301 subject identifier are populated across records.
- By-subject listings display subject identifier, but not unique subject identifier.

7.5 eDiary Data

7.5.1 Study Medication

7.5.1.1 eDiary Migraine Report

If the subject answered “yes” to taking study medication mistakenly already before using the eDiary, then the eDiary Migraine Report collects study medication data based on when the subject reported taking study medication (today, yesterday, or other) as follows:

- Today: Study medication dose date is set to the finding date, and study medication dose time is collected
- Yesterday: Study medication dose date is set to the finding date – 1 day, and study medication dose time is collected
- Other: Only the study medication dose date is collected (time is missing).

The eDiary Migraine Report derives the study medication dose date and time from all available data.

Otherwise, if the subject answered “no” to taking study medication mistakenly already, had a current pain intensity of moderate or severe, and answered “yes” to confirming having taken study medication, then the eDiary Migraine Report derives the study medication dose date and time as the exact date and time the subject confirmed taking study medication (i.e., after the finding date/time).

7.5.1.2 eDiary Study Medication Intake Report

Subjects who took study medication without using the eDiary have the study medication date and time reported by the site on the eDiary Study Medication Intake Report.

